2.8 Sample size

Sample size will be 500 newly presenting postmenopausal women blood samples, allowing 5% for loss to follow up.

The Cancer Molecular Diagnostics Laboratory (CMDL) and Queen Mary University of London (QMUL) teams performing plasma ctDNA analysis and additional biomarker analysis will be blinded to the clinical dataset held at UoB. This is to eliminate bias in analysis of the samples and to test the validity of the biomarker. To ensure this the clinical dataset will be maintained in UoB and the team at UoB will supply research teams with the samples anonymised with participant study numbers only. Research teams will send UoB the results of the analysis and the UoB and statistical team will then check that against outcome data to analyse trial outcomes.

2.9 ROCKETS-GEN V2 Outcome measures

Sensitivity and specificity of plasma ctDNA analysis in the diagnosis of OC. See 2.6 ROCKETS GEN V2 analysis.

2.10 Schedule of Events & CRF completion for ROCKETS-GEN V2

Table 1: Schedule of events and CRF completion

	Screening	Baseline	≤ 12 months
Eligibility Check	x ¹		
Valid Informed Consent	x ¹		
Registration Form CRF		x	
Online registration		x ²	
GP Letter		x	

Blood sample		x ⁴	
IOTA USG		Optional	
Ultrasound CRF		Optional	
Participant Baseline CRF		x ³	
Surgery CRF			Post-surgery/biopsy
Representative tissue block/s			x ⁵
Outcome CRF			12 months – only required if histology/cytology not obtained

¹ See section 'Approaching Potential Participants to Consent'.

² It is acceptable to delay registration until blood sample, IOTA USG & Participant Baseline CRF are complete.

³ Blood sample, IOTA USG and Participant Baseline CRF should all be captured within 3 months of whichever of the following occurred first: presentation, IOTA USG (see section 5.1).

⁴ Blood samples including dried blood spots, serum and plasma, send immediately to CMDL

⁵ Tissue sample (if participant proceeds to surgery) or biopsy send to Central study lab (CMDL or QMUL).

3 SELECTION OF PARTICIPANTS

3.1 Source of potential participants

Patients referred as Outpatients; either as 2 week or routine referrals, USG clinics, inpatient and emergency presentation to secondary care. Patients proceeding to surgery attending preadmission clinics. Patients proceeding to biopsy. Only postmenopausal women with suspected OC should be considered for ROCKeTS GEN V2. Participants can also be recruited into the study on the morning of surgery if there has not been a previous opportunity to recruit.

These should be new patients only, i.e. first presentation to the service; patients who are on routine follow up in the secondary care service as part of standard practice should not be approached for recruitment.

ROCKeTS GEN V2 will only recruit postmenopausal women.

3.2 Inclusion and Exclusion Criteria

3.2.1 Inclusion criteria

- Women referred with symptoms of suspected OC (typical referral symptoms are defined in section 2.5 of the protocol).
- Only postmenopausal women are included.
Menopause is defined as >12 months without menstruation. Those no longer menstruating >12 months for reasons such as contraception or hysterectomy should

have their menopausal status categorised according to age; <50 years premenopausal, 51+ years postmenopausal.

- In addition, women must have test results from one of the following:
 - 1) A raised CA125 test result (even if imaging has not been done yet)
 - 2) Abnormal imaging result showing a lesion (even if CA125 test is not raised).
 - 3) Both a raised CA125 test and an abnormal imaging result showing a lesion
- Patients able to provide informed consent.

FOR THIS STUDY WE FOLLOW THE IOTA DEFINITION OF A LESION: A LESION IS PART OF AN OVARY OR AN ADNEXAL MASS THAT IS JUDGED TO BE INCONSISTENT WITH NORMAL PHYSIOLOGICAL FUNCTION.

3.2.2 Exclusion criteria

- Premenopausal women
- USG reveals simple ovarian cysts <5cm in size (very low risk of malignancy) and patient does not have a raised CA125.
- Previous ovarian malignancy.
- Active non ovarian malignancy – Women with a past history of cancer are only eligible if there are no documented persistent or recurrent disease and they have not received treatment for this in the last 12 months. This exclusion does not apply to patients with premalignant disease e.g. cervical intra-epithelial neoplasia or patients receiving Tamoxifen/other drugs to prevent breast cancer recurrence.

3.3 Approaching potential participants for consent

Potential participants can be approached ahead of their clinic appointment or at their clinic appointment or whilst they are inpatients in hospital. Eligible patients may also be identified at scan departments. If potential participants cannot be approached at this time, then remote or virtual consent can be obtained as documented in 3.4. A member of the research team or usual care team will approach patients via phone or remotely. The approach process will parallel the in-person process.

If they are interested, they will be supplied with the participant information sheet (PIS) and given the opportunity to ask any questions.

Patients who are admitted into hospital as emergencies and undergoing investigations for OC will be approached to give informed consent. In our experience, these patients are unwell enough to need hospital stay but are not critically unwell to the extent that they cannot fully understand the implications of consent.

This study can be led by nursing or allied health care professional staff. Consent should be sought under unhurried circumstances – however consent can be obtained on the same day the potential participant is approached (i.e. the potential participant may choose to consent on the day that they receive their PIS or take time to reflect and consent at a later date) when entry criteria are fulfilled. Patients can also be approached on day of surgery or biopsy as study participation has no change in clinical pathway and involves sample collection only. Consent will be sought as follows:

- A PIS will be given to all women referred through rapid access 2 week wait clinics, USG and outpatient clinics and pre-admission clinics for suspected OC. This PIS and posters on the study will also be made generally available and prominently displayed in various areas within the participating hospitals and their primary care practices – including clinics, corridors, MDT meeting rooms, ultrasound rooms, offices. PIS are also available via the trial website. All women presenting as acute admissions to hospital will be offered the PIS and the option of study participation, unless deemed inappropriate by the attending clinical team for clinical reasons. However, wherever possible the patient should make the decision on whether to receive the study information or not.
- A potential participant can also be approached over the telephone/video call. Once the potential participant has shown interest in the study the PIS, Informed Consent Form (ICF) and baseline participant booklet can also be sent out for them to read at home. The site staff will then follow this up with remote consent as documented in 3.4.
- A potential participant can also be approached on the morning of surgery if it is not possible to approach in clinic or by remote consent before this time. They will be given the PIS and enough time to read the information before consent takes place.
- Patients admitted for investigations or as emergency admissions will be approached. They will be given the PIS and enough time to read the information before consent takes place.
- Where necessary, appropriate trust interpreters will be asked to aid discussion relating to study participation. Patients who do not understand English are eligible to enter the study provided an interpreter can fully explain the ICF and PIS to them.
- The initial approach to the potential participant will be through their clinician or appropriately trained person delegated the responsibility to approach patients to discuss the study. The consent form will be signed by the patient prior to any dried blood spot, serum or plasma samples being taken and counter signed by the person delegated the responsibility of taking consent.
 - If the scan is part of the standard care pathway, participants may receive an USG prior to consent as part of usual care. Data from these scans can be collected retrospectively into the study. As the British Gynaecological cancer society has recommended IOTA ADNEX ultrasound in their guidance on management of women with cysts, it is likely that at some sites patients will have the scan performed prior to study entry³⁸. For ROCKETS-GEN V2 the IOTA scan is optional.
- For patients who have already attended a hospital visit and who have not been given a PIS, the research team member can approach them by phone to provide information about the study.

3.4 Obtaining consent

The participant's written informed consent to participate in the study will be obtained before entry and after a full explanation has been given of the study. PIS and ICF will be provided so that patients can find out more about the study before deciding whether or not to participate.

- Visits throughout the informed consent process will take place in person at site or by telephone/video call as per local practice where patient and/or public health circumstances dictate. Signed informed consent forms can be completed in person or remotely if the circumstances dictate.

[figure not shown]
- If consent is not being taken in person, then the patient should be sent a PIS and ICF if not already supplied; then the clinical staff or delegated person will talk through each statement of the ICF with the patient, who will be asked to initial the boxes on the ICF and sign and date the form whilst on the call. This will be documented in the clinical notes. The ICF will then be returned to the clinical site for countersignature by the person who took consent remotely and the date the ICF was countersigned will be documented. Once a fully signed ICF has been completed it will be stored in the Investigator Site File and a copy will be sent to the Study Office and to the participant for their records. The participant baseline booklet can also be returned with the ICF.
- Participants will be assigned a study trial number after registration.

3.4.1 Informing the participant's GP

The participant's GP should be notified with the participant's consent and a specimen being sent to QMUL and CMDL. "GP Letter" is supplied.

4 RECRUITMENT

4.1 Flow chart for ROCKeTS GEN V2

4.2 Recruitment for ROCKeTS GEN V2

To obtain the large number of participants necessary for the reliable evaluation of the index tests, the study will need the participation of more than one centre. Study procedures therefore need to be kept simple, with minimal extra workload placed on participating clinicians, beyond that required to manage their patients. This will be achieved by simple entry procedures, early consent of women, the use of standard local testing regimens, minimising documentation and streamlining data collected procedures. Regular newsletters will keep collaborators informed of study progress, and regular meetings will be held to report progress of the study and to address any problems encountered in the conduct of the study.

4.3 Organisation of recruitment

Recruitment will be organised and supported by dedicated research team members who will work with local lead investigators. We believe that that the following strategy is likely to be successful in achieving maximum recruitment.

- **Whilst some participants in ROCKeTS GEN V2 will receive an IOTA ultrasound, the relevant scanner does not need to be IOTA certified.**
- **Eligibility for the study will be confirmed by clinical team members. Recruitment and study procedures can be performed by the research team.**
- Identification of appropriate research staff (doctors, clinical nurse specialists, research nurses, sonographers).
- A research team member at each site with responsibility for consent and study specific procedures.
- As part of the standard care pathway participants may receive an USG prior to consent and the data from these scans can be collected retrospectively.
- For participants in ROCKeTS GEN V2 the IOTA scan is not mandatory. If an IOTA ultrasound is performed as part of routine care, then we will collect that data as part of ROCKeTS GEN v2.
- Appointment of a trial manager at University of Birmingham, who will liaise with all the coordinating research nurses at each site and coordinate the screening at this hospital, provide training and trouble-shoot recruitment and follow-up problems.
- Provision of simple written study information, supported by face-to-face discussion with clinical staff.
- Provision of regular feedback on progress in study recruitment, including individual hospital teams' performance and progress against targets.
- Regular newsletters to all relevant staff involved in the study.

4.4 Other management at discretion of local doctors

Apart from the study tests, all other aspects of participant management are entirely at the discretion of the local doctors and as per the RCOG/BGCS guidelines for management of these participants.^{9,19} Treating clinicians will be asked to record their treatment recommendations as per standard care.

4.5 Withdrawal

Participants will be free to withdraw from the study at any time without any effect on standard of care; data and samples provided up to the point a participant withdraws will be retained.

5 STUDY PROCEDURES AND TESTS

5.1 Assessments for ROCKeTS GEN V2

Whilst symptoms are routinely elicited and recorded as part of a clinical assessment at presentation to secondary care, this is not standardised and involves the doctor transcribing elicited symptoms from the participant. Study participants entering the study will complete a baseline CRF.

A transabdominal and transvaginal USG is always performed for all patients suspected of OC as part of NICE guidelines. This is usually performed by trained ultrasonographers who report the scan as per routine. **For ROCKeTS-GEN V2 a transvaginal scan recording IOTA variables is not mandatory, but desirable if data available as part of standard of care.**

Participants will have an additional dried blood spot, serum and plasma sample taken at baseline for ctDNA and proteomics analysis. Details of sample collection will be provided in the lab manual.

5.2 Reference standard/Follow-up schedule

Reference standard for the study will be histology of tissue taken at surgery or biopsy or cytology in women who are managed surgically following study enrolment. Outcome of participants referred for suspected OC that do not undergo surgery will be assessed by a follow-up visit at 12 months or by a telephone call from the research team at 12 months, as per the local investigators' discretion and clinical assessment. Wellbeing will be ascertained at this follow-up.

5.3 Study duration

For **ROCKeTS GEN V2 participants** we anticipate recruitment of 500 participants. The current recruitment end date for ROCKeTS is 3 years from when the study is open at sites. It is anticipated that the recruitment will take 2 years. The follow-up will be 12 months from recruitment of last patient.

As per protocol, where histology is unavailable, participants should be followed up for the full 12 months, however the study recognises that for participants recruited within the last 12 months of the recruitment period the full 12 month follow-up will not be possible; instead, these participants should only be followed up until the end of study period.

The end of the ROCKeTS GEN V2 study, will be the date of the last data capture including sample analysis and resolution of all data clarification forms. This will allow sufficient time for the completion of protocol procedures, data collection and data input. The Trial Office will notify the REC and the Sponsor within 90 days of the end of trial. Where the trial has terminated early, the Trial Office will notify the REC within 15 days of the end of trial. The Trial Office will provide the REC and the Sponsor with a summary of the clinical trial report within 12 months of the end of trial.

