2.2 Design

ROCKETS GEN V2 study is a prospective single arm cohort diagnostic accuracy study where all patients receive all tests and accuracy of tests is evaluated against a gold standard of histology or 12-month outcome.

A test accuracy study compares measurements obtained by index tests with those obtained by a reference standard. In this way the accuracy of index tests can be estimated. A reference standard is a test (or combination of tests) that confirms or refutes the presence or absence of disease beyond reasonable doubt.

Here, the reference standard will be histology or cytology of tissues taken from patients who proceed to surgery or biopsy, or in patients who do not undergo surgery or biopsy assessment of cancer/non cancer outcomes determined from hospital records at 12 months. The diagnostic performance of the index test will be compared against that of the comparator test – the existing standard risk prediction score RMI 1. RMI combines CA125 and limited ultrasound features to provide a score that is used to determine patient management.^{3,37}

ROCKETS GEN V2 will recruit postmenopausal women at 'low' or unknown genetic risk of ovarian cancer i.e. not women known to have a BRCA1/2 or other germline mutation predisposing to ovarian cancer.

Recruited women will have the following tests and follow up recorded:

- CA125 (if not performed already as part of standard care).
- IOTA transvaginal ultrasound and additional abdominal scan if performed as part of standard care
- Histology result where biopsy or surgery is clinically indicated
- 12 month follow up status ascertained by research team using hospital records, a telephone call or by contacting GP.
- Women entering ROCKETS-GEN V2 will donate dried blood spots, blood samples for plasma and serum analysis at recruitment. Women undergoing surgery for ovarian pathology will also be consented to donate tissue block/s of representative tissue for research.

Representative tissue block/s and slide will be retrieved from pathology labs and proceeding to undergo surgery as part of standard care. These blocks will first undergo specialist pathology review by an expert gynaecological pathologist. DNA will then be extracted from cancer tissues for additional analyses including shallow whole genome sequencing.

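### Section 5.3 promises 12 months of follow-up past the last recruit, then shortens it for late recruits without histology, against the 12-month reference standard

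*Protocol*

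**What the plan says.** Section 5.3 of the protocol makes these statements about timing:

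- On recruitment: "The current recruitment end date for ROCKeTS is 3 years from when the study is open at sites", followed by "It is anticipated that the recruitment will take 2 years".
- On the follow-up tail: "The follow-up will be 12 months from recruitment of last patient".
- On women without histology: "where histology is unavailable, participants should be followed up for the full 12 months".
- On late recruits, as an exception to the line above: "for participants recruited within the last 12 months of the recruitment period the full 12 month follow-up will not be possible".
- On what happens to them: "instead, these participants should only be followed up until the end of study period".

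The section then dates the end of the study by the last data capture, which includes sample analysis and the closing of data queries.

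Elsewhere the 12-month point is part of the reference standard. Section 2.2 says "accuracy of tests is evaluated against a gold standard of histology or 12-month outcome". Sections 2.7 and 5.2 repeat the 12-month assessment for women who do not have surgery, and Table 1 places the Outcome CRF at 12 months when there is no histology or cytology. Section 5.7.1 says that imputation will deal with missing data and with imperfect reference results.

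**The concern.** A tail of 12 months after the last recruit gives every participant at least 12 months. If that tail exists, a full year is possible for women recruited in the final 12 months, and the exception has no one to apply to. If the exception applies, the tail does not exist. A site or data manager cannot follow both.

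The conflict affects the reference standard itself. For a woman with no tissue diagnosis, the 12-month outcome is the only thing that decides whether she counts as a case. The exception replaces it with a shorter period that has no stated minimum and no matching time point in Table 1. The stopping point is also hard to apply, because the end of the study is itself dated by the last data capture.

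If a cancer has not been diagnosed by a shortened check, the woman may be recorded as non-cancer. A correct positive ctDNA or RMI result would then be scored as a false positive, lowering specificity and PPV. A false negative would be scored as a true negative, raising NPV. In either case a true case would drop out of the sensitivity denominator.

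**Working it through.** **Inputs**

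- Planned sample: 500, with 5% loss to follow-up (section 2.8: "Sample size will be 500 newly presenting postmenopausal women blood samples, allowing 5% for loss to follow up").
- Share not sent for surgery or biopsy: 10-15%; number analysed: about 406; prevalence: 27%, giving 110 cancers (section 5.7.2).
- Recruitment: 2 years anticipated, 3 years to the stated end date (section 5.3).
- Assumptions made here, not in the protocol: uniform accrual, and the 10-15% taken as the share of women without histology.

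**Step 1. Reproduce the plan's own figures.** Analysed = 500 × 0.95 × (1 − q), where q is the share without surgery or biopsy.

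- q = 10%: 427.5
- q = 14.5%: 406.1
- q = 15%: 403.75

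So 406 is recovered near the upper end of the range, and 406 × 0.27 = 109.6, or 110 cancers. The inputs are being read as the protocol intends.

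**Step 2. Share recruited in the last 12 months.**

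- 2-year recruitment: 12/24 = 50%, or 250 of 500.
- 3-year recruitment: 12/36 = 33%, or 167 of 500.

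**Step 3. Late recruits without histology, if follow-up stops when recruitment closes.** The lower end uses the 475 left after 5% loss (500 × 0.95) and q = 10%. The upper end uses 500 and q = 15%.

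| Recruitment | Lower end | Upper end |
|---|---|---|
| 2 years | 475 × 0.10 × 0.5 = 23.75 (24) | 500 × 0.15 × 0.5 = 37.5 (38) |
| 3 years | 475 × 0.10 / 3 = 15.8 (16) | 500 × 0.15 / 3 = 25 |

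That is about 3% (15.8/500) to 8% (37.5/500) of the cohort. Their follow-up would run from 0 to 12 months, about 6 on average.

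**Step 4. The same count under other readings of when the study ends.**

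- Study runs 12 months past the last recruit: 0 women affected.
- Study closes at a fixed month 36 (an assumption; the text does not say this). The number recruited after month 24 is 500 × (R − 24)/R for a recruitment lasting R months:
  - R = 24: 0 women.
  - R = 30: 500 × 6/30 = 100 late recruits, 10-15 without histology.
  - R = 36: 500 × 12/36 = 167 late recruits, 17-25 without histology.

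The number affected therefore runs from 0 to 38, depending on which sentence governs and when follow-up stops.

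**The case against.** Several points on the other side are sound and limit what can be claimed.

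- **Scope.** The exception covers only late recruits without histology. A reader might infer that everyone recruited in the final year loses follow-up. The text does not say that, and the count in the working is restricted accordingly.
- **Classification.** A reader might infer that these women are counted as cancer-free. The protocol does not say so. Section 5.7.1 promises imputation for missing and imperfect reference results, and the detail may sit in an analysis plan that is not shown. What remains is that section 5.7.1 does not say a shortened follow-up counts as missing or imperfect, so a non-cancer record made early need not trigger imputation.
- **Role in the primary analysis.** Section 5.7.2 takes off the women not sent for surgery or biopsy before it reaches 406, and these are largely the same women. Contamination of the primary estimate therefore cannot be asserted. Sections 2.2 and 2.7 nevertheless make the 12-month outcome the reference standard for exactly these women, so their role is unclear.
- **Effect on sensitivity.** Section 5.7.2 implies about 19 early-stage HGSOC (110 × 0.70 × 0.25 = 19.25), and it is tempting to say that one missed case moves sensitivity by 1/19, about 5 points. That is wrong for this mechanism, because a case recorded as non-cancer also leaves the denominator. As an illustration, losing one test-positive case turns 15/19 (78.9%) into 14/18 (77.8%), about 1 point.
- **Length of the cut.** The 6-month average holds only if follow-up stops at recruitment close. The study's end date includes sample analysis, so follow-up could run later by an unstated amount.
- **Possible origin.** The 3-year recruitment end date beside an anticipated 2-year recruitment may explain the exception. The text does not say so, and the sentence promising 12 months past the last recruit would still be contradicted.

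None of this removes the contradiction. Nor is it a matter to leave to an analysis plan: the protocol itself sets the length of follow-up, and sets it two ways.

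**Conclusion.** The point holds as an internal contradiction in section 5.3 that leaves the reference standard undefined for some women. With uniform accrual and 10-15% lacking surgery or biopsy, about 24-38 women (2-year recruitment) or 16-25 (3-year) would have a shortened reference outcome if follow-up ends at recruitment close. If the 12-month tail governs, the number is zero.

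Misclassification of undiagnosed cancers as non-cancer is a risk, not a stated rule. It would bias specificity, PPV and NPV and could lose a true case. Its size cannot be computed, because the protocol gives no cancer rate among women without histology and does not say how a shortened outcome is classified.

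**What to change.** Reconcile the two statements in section 5.3. The direct way is to delete the truncation sentence and keep follow-up to 12 months after the last recruit for every woman without histology. This matches sections 2.2, 2.7 and 5.2 and Table 1, and the tail it needs is already stated in the same section.

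Add one line to section 5.7.1: a woman with no histology and under 12 months of follow-up has a missing or imperfect reference result, handled by the imputation already announced there, and is not entered as negative.

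The edit itself is two sentences. If the timeline really is constrained, the price is that a few late outcomes arrive later or are handled as missing.
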